17.1.1 All Adverse Events

Adverse events will be summarized in terms of frequency tables by worst National Cancer Institute – Common Terminology Criteria for Adverse Events (NCI-CTCAE) grade, primary

SOC body term as the Body System category and PT as the event category in alphabetical order. Both PT and SOC will be assigned using the latest version of MedDRA.

Each subject will be counted only once within each SOC and PT. If an adverse event is reported for a given subject more than once during treatment, the worst (i.e. maximum) severity and the strongest relationship to trial treatment will be summarized.

In case a subject had events with missing and non-missing grades, the maximum of the non-missing grades will be displayed. No imputation of missing grades will be performed.

An adverse events summary table will be provided. The rows of the summary table will show the overall number and percentage of subjects for each of the following:

- Any TEAE
- Trial treatment-related TEAEs
- Serious TEAEsTrial treatment-related serious TEAEs
- Non-serious TEAEs
- Trial treatment-related non-serious TEAEs
- Any TEAE by NCI-CTCAE severity grade ($\geq 3, \geq 4$)
- Trial treatment-related TEAEs by NCI-CTCAE severity grade ($\geq 3, \geq 4$)
- TEAEs of special interest (AESI)
- Trial treatment related AESIs
- TEAEs leading to temporary treatment discontinuation
- Trial treatment-related TEAEs leading to temporary treatment discontinuation
- TEAEs leading to permanent treatment discontinuation
- Trial treatment-related TEAEs leading to permanent treatment discontinuation
- TEAEs leading to death
- Trial treatment related TEAEs leading to death

Additionally, frequency tables by primary SOC and PT will be presented for the above, except for (related) TEAEs leading to death, which will be presented in a listing.

17.1.2 Adverse Events Leading to Treatment Discontinuation

See Section 17.1.1.

17.2 Deaths, Other Serious Adverse Events, and Other Significant Adverse Events

17.2.1 **Deaths**

All deaths and deaths within 33 days after last dose of trial treatment and deaths within 60 days after first trial treatment, as well as "reason for death", will be tabulated based on information from the "Death" and "Survival Follow-Up" eCRFs.

In addition, date and primary reason for death will be provided in an individual subject data listing along with selected dosing information (date of first / last administration of trial treatment). The listing will include a column for AEs with a fatal outcome and will identify deaths that occurred within 33 days of that subject's last administration of trial treatment and within 60 days after first trial treatment.

17.2.2 Serious Adverse Events

Please refer to Section 17.1.1. A subject listing of all SAEs will be provided in addition to the table described in Section 17.1.1.

17.3 Clinical Laboratory Evaluation

Laboratory results are assessed at a local laboratory and will be classified using NCI-CTCAE Version 4.0.

The following will be presented:

- Tables with descriptive statistics and boxplots for both chemistry and hematology values and their changes from baseline by visit
- An evaluation of Drug-Induced Serious Hepatotoxicity (eDISH) plot for total bilirubin and alanine aminotransferase (ALT)
- An eDISH plot for total bilirubin and aspartate aminotransferase (AST)
- For NCI-CTCAE gradable chemistry and hematology parameters:
 - O Tables for the worst grade (≥ 0 , ≥ 3 , or ≥ 4) during the on-treatment period using counts and percentages by laboratory parameter
 - Tables showing shifts from baseline to highest (worst) on-treatment grade (0, 1, 2, 3, or 4) For those parameters which are graded for increase as well as

decrease such as potassium (hypokalemia/hyperkalemia), the toxicities will be summarized separately.

- For non NCI-CTCAE gradable chemistry and hematology parameters:
 - Tables displaying shifts from baseline to abnormal values for the maximum and minimum post-baseline values based on reference range (Low, Normal, or High)

The following hematology parameters were collected:

- Hemoglobin
- Hematocrit
- Red blood cell count
- White blood cell count
- Differential white blood cell count
- Platelet count

The following chemistry parameters were collected:

- Blood urea nitrogen (BUN)
- Urea
- Creatinine
- ALT
- AST
- Gamma-glutamyl transpeptidase (GGT)
- Total bilirubin
- Direct fraction of bilirubin (if total is abnormal)
- Lipase
- Amylase
- Total Protein
- Albumin
- Alkaline Phosphatase
- Creatinine Clearance
- Sodium
- Potassium

- Calcium
- Magnesium
- Glucose

The following laboratory parameters collected on the eCRF will be listed in dedicated listings presenting all corresponding collected information:

- Coagulation: prothrombin time, activated partial thromboplastin time (aPTT), and International Normalized Ratio (INR)
- Pregnancy Tests: serum and urine
- Urinalysis: glucose, ketones, blood, pH, proteins, nitrites, leukocytes, and microscopic examination if abnormal urinalysis results
- HBV panel and anti-HCV (hepatitis C virus) antibodies: HBsAg (hepatitis B surface antigen), HBeAg (hepatitis B e antigen), anti-HBc (anti-hepatitis B core antigen), and anti-HCV
- Viral load of HBV/HCV (only for subjects with hepatitis B or hepatitis C, respectively, at screening)
- Tumor markers: serum AFP

Listings of laboratory results will be provided for all laboratory parameters with corresponding normal ranges. These listings will be sorted by parameter and visit for each subject.

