# 5.2 Discussion of Trial Design

The design of this trial is based on the safety, tolerability, and PK data observed in the FIM trial conducted with solid tumor subjects. Data from the FIM trial (EMR 200095-001) have revealed no safety and/or tolerability concerns thus far (refer to the current IB). The SMC proposed a dose of 500 mg administered once daily over a 21-day cycle as the RP2D for MSC2156119J. This RP2D is based on nonclinical PK/Pd modelling, which was supported by data on target inhibition from paired tumor biopsies.

In the current trial, a safety run-in phase will start dose escalation at 300 mg, thereby allowing for an additional safety step before exposing subjects to the full RP2D. Since liver/bile ducts have been identified as the main target organ in toxicology studies in dogs, and since it is expected that the majority of HCC subjects present with a history of chronic liver disease such as viral hepatitis or cirrhosis, careful monitoring of liver enzymes, hepatitis B virus (HBV) and hepatitis C virus (HCV) viral load, bile related parameters and other lab parameters and clinical signs related to viral reactivation, hepatitis flare, liver function degradation will therefore be implemented.

This trial uses standard measurements and assessments of HCC and tumors. The single-arm design is selected based on historical data with best supportive care after sorafenib failure or intolerance, which has been consistent across multiple studies (see Section 3.4). The decision to conduct this trial of MSC2156119J as second-line treatment is due to the relatively widespread use of sorafenib as a first-line treatment in Europe and the US.

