#### Table 1Hematology Assessments

Parameter
Hemoglobin (Hb)
Hematocrit (Hct)
Red blood cell (RBC) count
White blood cell (WBC) count
Differential WBC
Neutrophils
Eosinophils
Basophils
Monocytes
Lymphocytes
• Other
Platelet count
Prothrombin time (PT)
Activated thromboplastin time (aPTT)
International normalized ratio (INR)

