#### 8.5.4 Safety Analyses

Any treatment emergent AEs will be summarized, i.e., those events that are emergent during treatment having been absent pretreatment, or worsen relative to the pretreatment state and with onset dates occurring within the first dosing day of study treatment until 33 days after the last dose of study treatment. No formal statistical comparisons are planned.

The extent of exposure to MSC2156119J will be characterized by time on treatment, number of initiated and completed cycles, actual cumulative dose (mg) and compliance (%).

AEs will be coded according to the Medical Dictionary for Regulatory Activities (MedDRA). Severity of AEs will be graded using NCI-CTCAE (Version 4.0) toxicity grade. The incidence of treatment-emergent AEs, SAEs, related AEs and SAEs, AEs of Grade  $\geq$  3 by NCI-CTCAE, related AEs of Grade  $\geq$  3 by NCI-CTCAE, AEs leading to permanent treatment discontinuation will be summarized by MedDRA system organ classes and preferred terms. AE summaries will be prepared for Cycle 1 and the whole treatment period.

All deaths and deaths within 33 days after last dose of study treatment as well as reasons for death will be tabulated.

Descriptive summaries of actual (absolute) laboratory values and changes from baseline will be presented. Laboratory results will be classified by grade according to NCI-CTCAE, Version 4.0. The worst on-treatment grades after the first dose of trial treatment will be summarized. Shifts in NCI-CTCAE grades from baseline to worst on-treatment grade and from baseline to end of treatment (day of final dose of MSC2156119J) will be presented.

Changes from baseline to minimum and maximum on-treatment values will be summarized descriptively for vital signs (body temperature, heart rate, and blood pressure) and body weight. Similarly, change from baseline to worst on-treatment value will be summarized descriptively for the QTc interval.

Clinically significant, abnormal findings from 12-lead ECG during treatment phase will be descriptively presented.

The baseline results of the physical examination will be presented. Clinically significant, abnormal findings from the physical examination are to be reported as AEs. Separate summaries of the physical examination during and after treatment will not be provided.

The ECOG performance score will be summarized descriptively by visit.

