13.4 Other Baseline Characteristics

The following baseline characteristics will be reported for this study:

- ECOG PS: 0 or 1
- c-Met Status: Immunohistochemistry (IHC) 0, IHC 1+, IHC 2+, IHC 3+
- c-Met Status: In Situ Hybridization (ISH): ISH+, ISH-
- HGF: Cancer-Associated Fibroblast (CAF)
- HGF: Cytoplasmic
- Alcohol use status: Never used, Regular user, Occasional user, or Former user
- Nicotine use status: Never used, Regular user, Occasional user, or Former user
- Height (cm)
- Weight (kg)
- Body Mass Index (kg/m²)
- Vascular invasion and/or extrahepatic spread: Presence or Absence
- AFP elevation at baseline: > 200 IU/mL or < 200 IU/mL
- Prior local-regional therapy: Yes or No
- Albumin-Bilirubin (ALBI) Grade (1): 1, 2, or 3

Specifications for computation:

- ALBI Grade (1):
 - O Calculate the linear predictor y: $y = (log_{10}(bilirubin) * 0.66) + (albumin * -0.085)$ where bilirubin is in μ mol/L and albumin is in g/L
 - o Compare y to the following cut points:

■ ALBI Grade 1: $y \le -2.60$

■ ALBI Grade 2: $-2.60 < y \le -1.39$

■ ALBI Grade 3: y > -1.39

• BMI (kg/m^2) = weight $(kg)/[height (m)]^2$

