17.3 Clinical Laboratory Evaluation

Laboratory results are assessed at a local laboratory and will be classified using NCI-CTCAE Version 4.0. Values that are below the limit of detection will be imputed as half of the detection limit.

The following will be presented:

- Tables with descriptive statistics and boxplots for both chemistry and hematology values and their changes from baseline by visit
- An eDISH (evaluation of drug-induced serious hepatotoxicity) plot for total bilirubin and ALT
- For NCI-CTCAE gradable chemistry and hematology parameters:
 - O Tables for the worst grade (≥ 0 , ≥ 3 , or ≥ 4) during the on-treatment period using counts and percentages by laboratory parameter
 - Tables showing shifts from baseline to highest (worst) on-treatment grade (0, 1, 2, 3, or 4) For those parameters which are graded for increase as well as decrease such as potassium (hypokalemia/hyperkalemia), the toxicities will be summarized separately.
- For non NCI-CTCAE gradable chemistry and hematology parameters:
 - Tables displaying shifts from baseline to abnormal values for the maximum and minimum post-baseline values based on reference range (Low, Normal, or High)

The following hematology parameters were collected:

- Hemoglobin
- Hematocrit
- Red blood cell count
- White blood cell count
- Differential WBC
- Platelet count

The following chemistry parameters were collected:

- Blood urea nitrogen (BUN)
- Urea
- Creatinine
- AST
- ALT
- Gamma-glutamyl transpeptidase (GGT)
- Total bilirubin
- Direct bilirubin (if total is abnormal)
- Lipase
- Amylase
- Total Protein
- Albumin
- Alkaline Phosphatase
- Creatinine Clearance
- Sodium
- Potassium
- Calcium
- Magnesium
- Glucose

The following laboratory parameters collected on the eCRF will be listed in dedicated listings presenting all corresponding collected information:

- Coagulation: prothrombin time, activated partial thromboplastin time (aPTT), and International Normalized Ratio (INR)
- Pregnancy Tests: serum and urine
- Urinalysis: glucose, ketones, blood, pH, proteins, nitrites, leukocytes, red blood cell count, white blood cell count

- HBV panel and anti-HCV (hepatitis C virus) antibodies: HBsAg (hepatitis B surface antigen), HBeAg (hepatitis B e antigen), anti-HBc (anti-hepatitis B core antigen), and anti-HCV
- Viral load of HBV/HCV (only for subjects with hepatitis B at screening)
- Tumor markers: serum AFP

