13.4 Other Baseline Characteristics

The following baseline characteristics will be reported for this study:

- Height (cm) (collected on the "Vital Signs" eCRF page)
- Weight (kg) (collected on the "Vital Signs" eCRF page)
- Body Mass Index (kg/m²) (derived as indicated below)
- ECOG PS: 0 or 1 (collected on the "ECOG Performance Status" eCRF page)
- FHSI-8 score (collected on the "FHSI-8" eCRF page)
- Functional Assessment of Cancer Therapy-Hepatobiliary (FACT-HP) score (collected on the "FACT-HP" eCRF page)

- Nicotine use status: Never used, Regular user, Occasional user, or Former user (collected on the "Nicotine Consumption" eCRF page)
- Alcohol use: Yes or No (collected on the "Alcohol Consumption" eCRF page)
- AFP elevation at baseline: ≥ 200 IU/mL or < 200 IU/mL (collected on the "Tumor Markers" eCRF page)
- Prior local-regional therapy: Yes or No (collected on the "Prior Anti-Cancer Local-Regional Therapy" eCRF page)
- Albumin-Bilirubin (ALBI) Grade (1): 1, 2, or 3 (derived as indicated below)

Specifications for computation:

- ALBI Grade (1):
 - O Calculate the linear predictor y: $y = (log_{10}(bilirubin) * 0.66) + (albumin * -0.085)$ where bilirubin is in μ mol/L and albumin is in g/L
 - o Compare y to the following cut points:
 - ALBI Grade 1: $y \le -2.60$
 - ALBI Grade 2: $-2.60 < y \le -1.39$
 - ALBI Grade 3: y > -1.39
- Body mass index (kg/m^2) = weight $(kg)/[height (m)]^2$

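### INR, PT and aPTT are listing-only in both SAPs, although the protocol plans summaries, worst grades and shifts for laboratory results without excepting coagulation

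*SAP*

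**What the plan says.** **Protocol.** Section 3.5 names hepatobiliary toxicity as a potential risk. Section 5.2 calls the liver and bile ducts the main target organ in dog toxicology and says that careful monitoring of laboratory parameters and "clinical signs related to viral reactivation, hepatitis flare, liver function degradation will therefore be implemented". Table 1, the hematology assessments, includes PT, aPTT and INR. Section 8.5.4 plans descriptive summaries of laboratory values and changes from baseline. It continues: "Laboratory results will be classified by grade according to NCI-CTCAE, Version 4.0". It then plans a summary of worst on-treatment grades and shifts from baseline to worst grade and to end of treatment. Coagulation is not excepted.

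**Both SAPs, Section 17.3.** By-visit tables, worst-grade tables and shift tables apply to chemistry and hematology parameters. The parameter lists that follow omit PT, aPTT and INR. A separate sentence reads "The following laboratory parameters collected on the eCRF will be listed in dedicated listings presenting all corresponding collected information", and its first item is coagulation with those three tests.

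**Both SAPs, Section 13.4.** The baseline characteristics include "Albumin-Bilirubin (ALBI) Grade (1): 1, 2, or 3", with formula and cut points. ALBI is not used after baseline.

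**Both SAPs, Section 9.** No legible item mentions coagulation. Both sections close by saying that the protocol's methods otherwise apply.

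**The concern.** INR bears directly on liver function in this trial. It is a component of the Child-Pugh table in Protocol Appendix D, and a value above 2.3 excludes a subject at entry. It is drawn with hematology and chemistry at screening and at the treatment, end-of-treatment and follow-up visits; at Cycle 1 Day 1 it is repeated only if the last sample is more than 7 days old. The data therefore exist, and the protocol's analysis section covers them, but the SAPs produce no count or proportion from them.

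The adverse event tables do not reliably fill the gap. Protocol 7.4.1.1 says that abnormal laboratory findings should not be reported as adverse events unless they come with signs and symptoms, lead to discontinuation, or are judged medically important. An asymptomatic INR rise that the investigator does not consider important would stay out of those tables. The eDISH plots use bilirubin and transaminases, not INR. The clinical trial report could then give no rate for coagulation worsening in a cirrhosis-prone population given a drug with a named hepatic risk.

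**Working it through.** The plan states no figure on this point, so the check is mainly a comparison of texts.

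**1. What each on-treatment liver measure gets**

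| Measure | By-visit change | Worst grade or range shift | Other |
|---|---|---|---|
| Total bilirubin | yes | yes | eDISH with ALT (both phases) and AST (Phase II) |
| ALT, AST | yes | yes | eDISH (ALT in both phases; AST in Phase II) |
| Albumin, GGT, alkaline phosphatase | yes | yes | none |
| PT, aPTT, INR | no | no | listing |
| ALBI grade | no | no | baseline only |

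Section 17.3 has a table type for either case: grade shifts for gradable parameters and reference-range shifts for the rest. Coagulation gets neither.

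**2. Is the narrowing declared?** Phase Ib SAP Section 9 has two items: physical examination results, and relative dose intensity in place of compliance. Phase II Section 9 has more items; none that can be read concerns coagulation, and one cannot be read. Non-declaration is therefore confirmed for Phase Ib and, for Phase II, only for the legible text.

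**3. What a rate would look like.** The documents give no counts, so these are assumed. The interval is the exact Clopper-Pearson 90% interval that the SAPs use for other rates. For x of n, the lower limit is the 5th percentile of Beta(x, n − x + 1) and the upper limit is the 95th percentile of Beta(x + 1, n − x).

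- 0 of 48: 0% (0 to 6.1%)
- 5 of 48: 10.4% (4.2% to 20.7%)
- 10 of 48: 20.8% (11.8% to 32.8%)
- 0 of 18, the Phase Ib maximum: 0% (0 to 15.3%)

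**4. Whether the single-parameter tables make ALBI redundant.** The formula in Section 13.4 is y = 0.66 × log10(bilirubin, µmol/L) − 0.085 × albumin (g/L). Grade 1 is y ≤ −2.60 and Grade 2 runs above that to −1.39.

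- Bilirubin 12, albumin 42: 0.712 − 3.570 = −2.858, Grade 1
- Bilirubin 20, albumin 36: 0.859 − 3.060 = −2.201, Grade 2
- Bilirubin 12, albumin 36: 0.712 − 3.060 = −2.348, Grade 2

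Assume local limits of about 20 µmol/L for bilirubin (upper) and 35 g/L for albumin (lower); the documents give none. Then neither component leaves its normal range while the ALBI grade worsens. By-visit tables would show the drift in means, but no planned table would count the subjects who crossed a grade.

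**The case against.** The strongest reply is that the plan already reports liver function on treatment. Bilirubin and albumin are Child-Pugh components and the two ALBI inputs, and both are tabulated with the enzymes. Bilirubin is on every eDISH plot. Hepatic or coagulation events that are symptomatic, lead to discontinuation or are medically important reach the adverse event tables. This stands. A reader might infer that on-treatment loss of liver function gets no rate or shift at all; the documents do not support that.

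A reader might also infer that the protocol promised on-treatment ALBI. It does not mention ALBI, and the SAPs introduce it only as a baseline descriptor. In a single-arm trial an ALBI shift could not separate drug effect from cirrhosis or tumour progression. Nor does Section 5.2 promise a table: it promises monitoring, and does not name INR.

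Finally, the reach of 8.5.4 can be argued. It does not mention coagulation by name. The synopsis safety endpoints name hematology, chemistry and urinalysis. Section 7.4.3.1 is titled for both hematology and coagulation, and details are left to the SAP. These points weaken the case without removing it. Table 1 itself is headed as hematology and contains the three tests, and 8.5.4 speaks of laboratory values and results without exception. An SAP may narrow that plan, but should say so in Section 9.

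The listings are usable: they are sorted by parameter and visit within subject and give normal ranges, and Phase Ib flags values outside them. They still yield no rate.

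**Conclusion.** The point holds in a limited form. Coagulation is listing-only in both SAPs. On the natural reading of Protocol Table 1 and Section 8.5.4, this narrows the protocol's laboratory analysis, and no legible Section 9 item declares it. It affects three tests in up to 18 + 48 = 66 treated subjects. Separately, no composite liver-function measure is analysed after baseline; that is a missed opportunity, not a broken commitment.

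The consequence is that coagulation worsening which is never recorded as an adverse event would have no reported proportion. How common that would be cannot be said from the documents, and 5 of 48 is only an illustration. The conclusion assumes that the unreadable Phase II bullet does not declare the change and that 8.5.4 covers all tests in Table 1. This is a gap in secondary safety reporting. It does not affect the primary endpoint, its test or the sample size. It is worth correcting because the hepatic risk is one that the protocol itself names.

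**What to change.** In Section 17.3 of both SAPs, add INR, PT and aPTT to the existing by-visit change, worst on-treatment grade and baseline-to-worst shift tables, using reference-range shifts where a parameter is not gradable. Keep the listings. If the sponsor prefers listings only, state and justify that in Section 9 as a change from the protocol.

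As an option, add a shift from baseline ALBI grade to worst on-treatment grade, applying the Section 13.4 formula to bilirubin and albumin from the same day. Present it descriptively, with a note that a single-arm trial cannot attribute the shift to the drug. A Child-Pugh shift is less practical, because the visit schedule shows no structured on-treatment record of ascites or encephalopathy grade.

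The cost is SAP wording and two or three extra tables. No new assessment, visit or data field is needed.

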17.4 Vital Signs

Vital sign data was collected on the "Vital Signs" eCRF page. For the definition of baseline, see Section 11.

Table 2. Categories of Change from Baseline for Vital Sign Parameters

Parameters, baseline categories	Categories of Change from Baseline
Body temperature increase < 37°C; 37 - <38°C; 38 - <39°C; 39 - <40°C; ≥ 40°C	< 1°C , 1-<2°C , 2-<3°C, ≥ 3 °C
Heart rate increase from baseline <100 bpm; ≥ 100 bpm	≤20 bpm, >20 – 40 bpm, >40 bpm
Heart rate decrease from baseline <100 bpm; ≥ 100 bpm	≤20 bpm, >20 – 40 bpm, >40 bpm
Systolic Blood Pressure (SBP) increase from baseline	≤20 mmHg, >20 − 40 mmHg, >40 mmHg

<140 mmHg; ≥ 140 mmHg	
SBP decrease from baseline <140 mmHg; ≥ 140 mmHg,	≤20 mmHg, >20 – 40 mmHg, >40 mmHg
Diastolic Blood Pressure (DBP) increase from baseline <90 mmHg; ≥ 90 mmHg	≤20 mmHg, >20 – 40 mmHg, >40 mmHg
DBP decrease from baseline <90 mmHg; ≥ 90 mmHg,	≤20 mmHg, >20 – 40 mmHg, >40 mmHg
Weight increase	<10%, ≥10%
Weight decrease	<10%, ≥10%

The following summaries will be prepared for vital sign parameters as grouped in Table 1:

- Maximal Shifts from baseline to worst-on treatment value (changes in categories, including total rows/columns)
- Listing of highest on-treatment change from baseline per subject
- Minimum and maximum absolute and change from baseline values

